9.4.3 Safety Analyses

Unless otherwise specified all safety analyses listed in [Table 14](#) will be based on the safety population. All safety parameters will be analyzed using descriptive statistics, summarized and presented in tables. Data will be summarized by dose and regimen (if applicable) within each part.

Table 14 Safety Statistical Analysis Methods

Endpoint	Statistical Analysis Methods
Adverse events	The original terms recorded on the eCRF by the Investigator for AEs will be coded by the Sponsor. Adverse events will be summarized by mapped term and appropriate thesaurus level. The severity of AEs will be graded according to the NCI CTCAE v5.0. Toxicity grade, seriousness, and relationship to study treatment will be presented, as well as summaries of deaths, AEs leading to death and premature withdrawal from study treatment. A glossary of AEs, medication(s), and procedures will be provided.
Clinical laboratory tests	All clinical laboratory data will be stored in the database in the units in which they were reported. Laboratory test values will be presented in International System of Units (SI units; Système International d'Unités) by individual listings with flagging of abnormal results.
Vital signs	Vital signs data will be presented by individual listings with flagging of values outside the normal ranges and flagging of abnormalities. In addition, tabular summaries will be used, as appropriate.
ECG data analysis	ECG data will be presented by individual listings. In addition, tabular summaries will be used, as appropriate.
Concomitant medications	The original terms recorded on the participant's eCRF by the Investigator for concomitant medications will be standardized by the Sponsor by utilizing a mapped term and appropriate drug dictionary level. Concomitant medications will be presented in summary tables and listings.
Nature and frequency of DLTs	DLT events will be presented by individual listings. The MTD will be estimated with an mCRM-EWOC using DLT evaluable participants. The MTD estimate will be presented along with 90% Credible Intervals.

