3. OBJECTIVES AND ENDPOINTS

The objectives and corresponding endpoints are provided in [Table 3](#).

Table 3 Objectives and Endpoints

Objectives	Endpoints
Primary	
To characterize the safety, tolerability, maximum-tolerated dose (MTD) and/or Recommended Phase 2 Dose (RP2D) of RO7296682	
 • Nature and frequency of AEs (with severity determined according to the National Cancer Institute Common Terminology Criteria for Adverse Events [NCI CTCAE] v5.0) • Nature and frequency of dose-limiting toxicities (DLTs)
Secondary	
To assess the preliminary anti-tumor activity of RO7296682	
 • Objective response rate (ORR) • Disease control rate (DCR); defined as ORR + stable disease [SD] rate • Duration of response (DoR) • Progression-free survival (PFS) 
All according to the Response Evaluation Criteria in Solid Tumors (RECIST) Version 1.1

Objectives	Endpoints
To investigate the PK profile of RO7296682	PK profiles and parameters derived for RO7296682 including but not limited to: 
 • Area under the curve (AUC), minimum concentration (C_{min}), maximum concentration (C_{max}), Clearance (CL), Volume of distribution at steady-state conditions (V_{ss}), Half-life ($t_{1/2}$), as appropriate, Time of maximum concentration (T_{max})
To evaluate the anti-drug immune response after treatment	
 • Incidence and titer of ADA during the study relative to the prevalence of ADA at baseline
To assess the PD effect of RO7296682 in blood and tumor tissue	
 • Treatment-induced changes in Treg levels in blood and/or tumor as compared to baseline. • Treatment-induced changes in Treg/Teff ratio in blood and/or tumor as compared to baseline.
Exploratory	
To characterize PD effects and duration of PD response following RO7296682 administration	
 • Changes in number, frequency, activation status, and distribution of blood and tumor infiltrating lymphocytes (TILs)
To evaluate the relationship between RO7296682 exposure and PD biomarkers	

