6.3 MEASURES TO MINIMIZE BIAS: RANDOMIZATION AND BLINDING

6.3.1 Method of Treatment Assignment

This is an open-label study with no randomization.

The Sponsor will be responsible for allocation of patient numbers using an interactive voice/web response system (IxRS) process. The log in information and directions for the IxRS will be provided to each site.

Participants who fulfill all of the inclusion criteria and none of the exclusion criteria are eligible to participate in the study and will be assigned to a treatment group/dose in consultation with the Sponsor.

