8.3 ADVERSE EVENTS AND SERIOUS ADVERSE EVENTS

The definitions of an AE or SAE can be found in [Appendix 2](#). The non-serious adverse events of special interest (AESI) and disease-related events and/or disease-related outcomes not qualifying as AEs or SAEs are discussed in Sections [8.3.6](#) and Section [8.3.7](#).

The Investigator and any qualified designees are responsible for ensuring that all AEs (including assessment of seriousness, severity, and causality; see [Appendix 2](#)) are recorded on the Adverse Event eCRF and reported to the Sponsor in accordance with instructions provided in this section and in [Appendix 2](#).

Procedures used for recording AEs are provided in [Appendix 3](#).

8.3.1 Time Period and Frequency for Collecting Adverse Event and Serious Adverse Event Information

The method of recording, evaluating, and assessing causality of AEs and SAEs and the procedures for completing and transmitting SAE reports are provided in [Appendix 2](#).

Investigators will seek information on AEs at each participant's contact. All AEs, whether reported by the participant or noted by study personnel, will be recorded in the participant's medical record and on the Adverse Event eCRF as follows:

After informed consent has been obtained **but prior to initiation of study treatment**, only SAEs caused by a protocol-mandated intervention should be reported (e.g., SAEs related to invasive procedures, such as biopsies). Any other AE should not be reported.

After initiation of study treatment, all AEs, regardless of relationship to study treatment, will be reported until last follow-up visit. AEs fulfilling the criteria in Section [4.1.3](#) and occurring within the DLT period as defined in Section [4.1.2.1](#) will be reported as DLT.

Post-study AEs and SAEs: The Investigator is not required to actively monitor participants for AEs after the end of the AE reporting period – that is, after the last follow-up visit.

However, if the Investigator learns of any SAE (including a death) or other AEs of concern that are believed to be related to prior treatment with study treatment, at any time after a participant has been discharged from the study, and the Investigator considers the event to be reasonably related to the study treatment or study participation, the Investigator must promptly notify the Sponsor. For the procedure of reporting, see [Appendix 2](#).

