8.11.2 Assessments during Treatment

Under no circumstances will participants who enroll in this study and have completed treatment as specified, be permitted to re-enroll in the study.

All assessments must be performed as per SoA (Section 1.3). Assessments scheduled on the day of study treatment administration should be performed prior to administration of study treatment, unless otherwise noted in the schedule of assessments.

Participants will be treated with study treatment, until disease progression, unacceptable toxicity, withdrawal of consent, or withdraw by Investigator. Participants may receive study treatment for a maximum of 24 months since C1D1.

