9.3 POPULATIONS FOR ANALYSES

For purposes of analysis, the following populations are defined in [Table 12](#).

Table 12 Analysis Populations

Analysis Population	Description
Efficacy	All participants who received at least one dose of RO7296682, and who have at least one baseline and one on-study tumor assessment. Participants who received at least one dose of study drug and discontinued the study because of progression before the first on-study tumor assessment will be considered as response-evaluable.
DLT evaluable	DLT evaluable participants are those who have completed the DLT period with two administrations of RO7296682 during the DLT period and without DLT, or participants reported with a DLT. This population will be used in the determination of the MTD and/or RP2D.
Safety	All participants randomized to study treatment (RO7296682) and who received at least one dose of the study treatment, whether prematurely withdrawn from the study or not, will be included in the safety analysis.
Pharmacokinetic	All participants who have received at least one dose of study treatment (RO7296682) and who have data from at least one post-dose sample will be included in the PK analysis population. Participants will be excluded from the PK analysis population if they significantly violate the inclusion or exclusion criteria, deviate significantly from the protocol, or if data are unavailable or incomplete which may influence the PK analysis. Excluded cases will be documented together with the reason for exclusion. All decisions on exclusions from the analysis will be made prior to database closure.
Immunogenicity	The immunogenicity analyses will include all participants with at least one ADA assessment, irrespective of whether or not the participant receives any treatment. Excluded cases will be documented together with the reason for exclusion.

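### By-dose AE frequencies, one of the two primary endpoints, are summarised over scheduled observation of about 3 to 27 months with no common window, so differences between doses can reflect time on study as well as dose.

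*Combined protocol and SAP*

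**What the plan says.** Section 3 (Table 3) lists two primary endpoints: the nature and frequency of AEs, and the nature and frequency of DLTs.

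For AEs, Section 8.3.1 states that after treatment starts "all AEs, regardless of relationship to study treatment, will be reported until last follow-up visit". Section 8.11.2 states: "Participants may receive study treatment for a maximum of 24 months since C1D1". Section 4.1.1 puts the safety follow-up visit 90 (± 7) days after the last dose and gives a maximum of 28 months on study per participant.

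For the analysis, Table 14 in Section 9.4.3 states: "Adverse events will be summarized by mapped term and appropriate thesaurus level". It adds grade, seriousness, relationship, deaths, and AEs leading to death or withdrawal from treatment. On grouping, the same section says: "Data will be summarized by dose and regimen (if applicable) within each part". Neither Section 9.4.3 nor any other readable part of Section 9 gives a fixed AE window, a rate per time at risk, a time-to-first-event summary or a summary of treatment duration by dose.

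DLTs are handled differently. Section 4.1.2.1 limits them to the period from the first dose to 7 days after the second. Table 14 estimates the MTD from DLT-evaluable participants only.

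Table 12 defines the safety set as "All participants randomized to study treatment (RO7296682) and who received at least one dose of the study treatment", while Section 6.3.1 says: "This is an open-label study with no randomization".

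**The concern.** The proportion of participants who ever had an event depends on how long they were watched. A dose at which people stop early, through toxicity or progression, has less time in which to record AEs; a dose at which people stay on treatment has more. Cohorts also open one after another, so at a data cut during escalation the earlier, lower doses have had longer potential follow-up than the newest, highest dose.

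This matters because Section 4.1 bases the RP2D on safety, tolerability and PK/PD. Sections 4.1.2.1 and 4.1.4 allow escalation to stop without an MTD. In that case the DLT model will not by itself separate the candidate doses, and the by-dose AE tables carry more weight. Toxicity that starts after the DLT period appears mainly in those tables.

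Intra-participant dose increases (Section 4.1.2.2) add a further ambiguity: Section 9.4.3 does not say to which dose an AE after such an increase belongs.

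**Working it through.** **1. The plan's own duration.** Using 365.25/12 = 30.44 days per month: 28 days of screening (0.92) + 24 months + 90 days (2.96) = 27.9 months. This reproduces the stated maximum of 28 months.

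**2. Scheduled AE observation.** Section 8.3.1 does not name the last follow-up visit. I take it as the 90-day safety visit, because the later survival contacts collect only survival status and new anti-cancer treatment.
- One dose only: 90 days = 2.96 months (2.7 to 3.2 with the ± 7 days).
- Full treatment: 24 + 2.96 = 26.96 months (26.7 to 27.2).
- Ratio: 26.96 / 2.96 = 9.1.

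The lower figure is the scheduled minimum. Death or withdrawal of consent (Section 7.2) can shorten it.

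**3. Effect on crude frequency when dose has no effect.** The hazards h and average times t are assumptions, since the documents give neither. Formula: P(at least one event) = 1 − exp(−h × t).

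| Hazard per month | 4 months | 12 months |
|---|---|---|
| 2% | 1 − exp(−0.08) = 7.7% | 1 − exp(−0.24) = 21.3% |
| 5% | 1 − exp(−0.20) = 18% | 1 − exp(−0.60) = 45% |
| 10% | 1 − exp(−0.40) = 33% | 1 − exp(−1.20) = 70% |

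**4. The same with treatment time varying within a dose group.** Assume exponential treatment time capped at 24 months, plus 90 days of follow-up, and average 1 − exp(−h × t) over that distribution.

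| Median treatment | Mean observation | h = 2% | h = 5% | h = 10% |
|---|---|---|---|---|
| 2 months | 5.8 months | 10.9% | 24.6% | 42.3% |
| 8 months | 13.1 months | 22.1% | 44.1% | 65.0% |

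**5. With a common window.** At 5% per month, 28 days (0.92 months) gives 1 − exp(−0.046) = 4.5%, and 8 weeks (56 days, 1.84 months) gives 1 − exp(−0.092) = 8.8%, whatever the time on treatment. Both windows fit the schedule. Even after a single dose, follow-up is planned to at least 90 − 7 = 83 days. On schedule, the first tumor assessment falls no earlier than 56 − 7 = 49 days after first dose and the next dose after that is at day 63, so an intra-participant increase should not fall inside 8 weeks.

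**6. Why the choice of time at risk matters if a rate is added.** Suppose the hazard is 5% per month until 28 days after the last dose and zero afterwards. Counting time to the 90-day visit gives approximately:
- one dose: 0.05 × 0.92 / 2.96 = 0.016 per month;
- 24 months of treatment: 0.05 × 24.92 / 26.96 = 0.046 per month.

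On-treatment risk is identical, yet the early stopper looks safer. Ending time at risk 28 days after the last dose returns 0.05 for both.

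**The case against.** The strongest reply is that this is a descriptive Phase 1 study. Section 9.1 plans no hypothesis testing, and Section 9.4.1 says comparability of treatment groups does not arise. Dose decisions do not rest on a crude table: Section 4.1.5 has AE, laboratory, dosing, response and PK/PD data reviewed participant by participant, so the decision-makers can see how long each person was treated. Table 14 also reports AEs leading to withdrawal, which partly guards against a poorly tolerated dose looking safe. Cohorts may have only three DLT-evaluable participants; in three people, 18% against 45% is about 0.5 against 1.4 participants, well within chance.

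Much of this stands. It makes the point one of interpretation, not of error rates, and it limits the harm during escalation. It does not remove the gap: the by-dose tables are the planned analysis of a primary endpoint, and readers will compare their columns.

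A reader might infer more than the documents support:
- **That the MTD is compromised.** It is not; DLTs have their own common window.
- **That by-dose differences will reflect time on study.** That needs time on study to differ by dose, and the documents give no such data.
- **That doses could differ by the whole 3-to-27-month span** (14% against 74% at 5% per month). Those are extremes for individual participants, not plausible dose-group averages.
- **That crude AE status feeds the exposure-safety work.** Section 9.4.4 makes that work optional, and Section 9.4.7 names no form of outcome.
- **That the safety set is empty because nobody is randomized.** This is a drafting slip in a plainly open-label study; the intended set is clear.

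**Conclusion.** The point holds in a limited form. The plan summarises AE frequency by dose over observation that can vary about nine-fold between participants, and provides nothing to separate time on study from dose. The DLT endpoint and the MTD estimate are untouched; the AE tables that help support the RP2D are exposed, most of all if escalation ends without an MTD.

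The size is conditional. Under an equal, constant hazard of 2% to 10% per month, a three-fold difference in average observation (4 against 12 months) roughly doubles or nearly triples the crude proportion with no dose effect. If average time on study turns out similar across doses, the distortion largely disappears, but the planned tables would not show which case applies. It is an inexpensive improvement worth making; it does not invalidate the design.

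**What to change.** In Section 9.4.3 and Table 14, keep the crude AE table and add, by dose assigned at enrolment:

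- **(a)** the proportion of participants with at least one AE, by term and grade, starting within a common window from first dose: 28 days, and 8 weeks;
- **(b)** treatment duration and observation time by dose.

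If a rate is also shown, use participants with a first event per participant-month at risk. End time at risk at the first event, the End of Treatment visit (28 days after last dose) or any intra-participant dose increase, whichever comes first. Counting first events also keeps one person's recurrences, which Appendix 3 records separately, from dominating a small cohort.

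As tidying only, delete the reference to being randomized from the Table 12 safety set, leaving all participants who received at least one dose.

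The cost is one or two more tables from data already collected, with no change to sample size or conduct. The fixed window misses late events, which stay in the crude table. The rate, if used, assumes a roughly constant hazard.

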9.4.4 Pharmacokinetic Analyses

Regular PK sampling will be performed in this study to properly characterize the PK of RO7296682.

When appropriate, PK parameters will be derived from the serum concentrations of RO7296682 using standard non-compartmental methods.

Individual and mean serum RO7296682 concentration versus time data will be tabulated and plotted by dose levels and/or dosing regimens. All PK parameters will be presented by listings and descriptive summary statistics separately by dose levels and/or dosing regimens.

Parameters may include, for example, AUC, CL, and volume of distribution under steady-state conditions, as appropriate. These parameters will be tabulated and summarized (mean, standard deviation, coefficient of variation, median, minimum, and maximum). Inter-participant variability and drug accumulation will be evaluated.

Non-linear mixed effect modeling will be used to analyze the concentration-time data of RO7296682. For RO7296682, population and individual PK parameters may be

estimated, and the influence of various covariates (such as age, gender, and body weight) on these parameters may be investigated in an exploratory way. Secondary PK parameters (such as C_{max} and AUC) may be derived from the model for each individual included in the PK analysis and will be presented descriptively.

Additionally, exploratory analyses on exposure and safety/efficacy relationship may be conducted if deemed necessary. The details of the modeling and exploratory analyses will be reported in a document separate from the CSR.

9.4.5 Immunogenicity Analyses

Antibodies against RO7296682 will be evaluated in serum samples collected from all participants using appropriate assays. Listings and/or summaries will be prepared. Additional analyses may be conducted as appropriate.

The immunogenicity analyses will include all participants with at least one ADA assessment, irrespective of whether or not the participant receives any treatment ([Shankar et al. 2014](#)).

The numbers and proportions of ADA-positive participants and ADA-negative participants at baseline (baseline prevalence) and after study drug administration (post baseline incidence during both the treatment and follow-up periods) will be summarized.

- Participants are considered to be ADA positive if they are ADA negative or missing data at baseline and develop an ADA response following study drug administration (treatment-induced ADA response), or if they are ADA positive at baseline and the titer of one or more post-baseline samples is greater than the titer of the baseline sample by a scientifically reasonable margin such as at least 4-fold (treatment-enhanced ADA response). Treatment-induced ADA response can be further categorized in persistent (post-treatment ADA-positive samples over 16 weeks or more or the last ADA time point is positive) and transient (only one ADA-positive sample or the time between the first and last ADA-positive sample is less than 16 weeks and the last ADA sample is negative).
- Participants are considered to be ADA negative if they are ADA negative or missing data at baseline and all post-baseline samples are negative, or if they are ADA positive at baseline but do not have any post-baseline samples with a titer that is greater than the titer of the baseline sample by a scientifically reasonable margin such as at least 4-fold (treatment unaffected).

The relationship between ADA status and safety, efficacy, PK, and biomarker endpoints may be analyzed and reported.

Additional analyses may be conducted as appropriate.

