		EOI ± 15min		x	x															
End of Treatment (EoT) Visit	28 days (± 7) after last dose	At vis t		x	x	x	x													
Safety FU (90d after last dose)		At vis t		x	x	x										x				
In addition, samples to be taken at the following instances:																				
In the event of an IRR ≥ G2 or hypersensitivity event or AE ≥ G3 leading to dose reduction or interruption		At vis t			x	x			x						Any visit					x
		At vis t																		
DLT		At vis t			x	x			x										x	
Unscheduled Visit ⁱ		At vis t			x	x	x	x	x										x	

Table 2 Schedule of Activities Q3W, Details (cont.)

a)	The time windows can be used for flexibility. For example if Day 2 occurs on a Friday, Day 4 can be conducted on the following Monday and Day 8 on the Thursday.
b)	During the course of the study, PK/PD sampling time points may be modified based on emerging data to ensure that PK/PD of RO7296682 can be adequately characterized. In this case, no new additional PK/PD samples will be introduced but sampling times may be modified. Blood for PK/PD should be drawn at the indicated time points.
c)	All blood samples for PK assessments will be collected from an IV line in the opposite arm to the one for drug infusion.
d)	Up to Cycle 5: PK and ADA samples should be taken at indicated time points . Subsequent cycles until 6 months after first dose of RO7296682: PK and ADA samples will be taken on Day 1 of each cycle. Subsequent cycles after first 6 months of RO7296682 treatment: PK and ADA samples will be taken only Day 1 at cycle of tumor assessments .
e)	Unscheduled PK samples will be taken (where feasible) at the time of development of any of the following events, or at the earliest possible convenience thereafter: * DLT * Dose reduction or treatment reduction or interruption due to IRR/CRS event \geq G2 or hypersensitivity event or AE \geq G3. - At time of interruption, collect the unscheduled PK sample and clearly record the reason for this collection (i.e., due to interruption). - At infusion restart and completion, collect scheduled pre, (mid – where applicable) and post infusion time points as noted per SoA.
f)	Tryptase and IgE samples will be collected for local analysis at onset of the reaction. A second sample for central IgE/Tryptase analysis will be collected approximately 48 hours after onset of the reaction.

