To evaluate preliminary anti-tumor activity of RO7296682 according to immune RECIST (iRECIST)	
 • Objective response rate (ORR) • Disease control rate (DCR); defined as ORR + SD rate All according to immune RECIST (iRECIST) 
In addition:
 
 • Duration of response (DoR) • Progression free survival (PFS) • Overall survival (OS) if data are mature
To explore potential effects of ADA	
 • Relationship between ADA status and PK/PD, safety, and efficacy

Objectives	Endpoints
To explore biologic markers that might act as predictors of safety and/or anti-tumor activity of RO7296682	
To explore degree of target binding of RO7296682 (in association with PK) via a receptor occupancy (RO) assay	
 Evaluate RO via ex-vivo assay
To explore the effect of Treg depletion in the skin immune contexture	
 Treatment-induced changes in Treg levels in the skin as compared to baseline.
To explore the effect of Treg depletion on the gut microbiome	
 Treatment-induced changes of the gut microbiome as compared to baseline

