8.6 IMMUNOGENICITY ASSESSMENTS

Although RO7296682 is a humanized antibody, there is a risk that ADAs against RO7296682 could develop, potentially reducing its efficacy and/or potentially resulting in symptomatic hypersensitivity reactions, in particular immune-complex reactions.

Validated screening, confirmatory, and titer assays will be employed to detect potential ADAs against RO7296682 at multiple time points before, during, and after treatment with RO7296682. If required, ADA-positive samples will be further characterized in exploratory assays.

[REDACTED]

If required, the residual volume of PK samples taken during the study (at any time point) can also be used for additional ADA analyses. Additional ADA samples will be drawn at the time of treatment discontinuation or at the safety follow-up visits and in participants who experience a Grade ≥ 2 IRR and in participants with clinical signs of hypersensitivity reaction, in particular immune-complex reactions. In any case, for each collected ADA sample, a corresponding PK sample will be collected at the same time point for the determination of the RO7296682 concentrations.

Any residual material from samples collected for PK, safety, biomarker assays, and ADA may be used for exploratory biomarker profiling, identification, and PK/PD assay development purposes and additional assessments (e.g. ADA response characterization), as appropriate.

The blood samples will be destroyed within 2 years after the date of the final CSR.

Details on sampling procedures, sample storage and shipment are given in the Study Flow Chart and Laboratory Manual.

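### ADA status is defined only as ever-positive over treatment and follow-up, so the optional ADA-efficacy comparison, if run with it, is biased in favour of ADA-positive participants

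*Combined protocol and SAP*

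**What the plan says.** Section 9.4.5 makes a participant ADA-positive if a treatment-induced or treatment-enhanced response appears in any post-baseline sample. Participants negative or missing at baseline are ADA-negative only if "all post-baseline samples are negative". The window is "post baseline incidence during both the treatment and follow-up periods".

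The same section adds: "The relationship between ADA status and safety, efficacy, PK, and biomarker endpoints may be analyzed and reported". Table 3 (Section 3) lists the matching exploratory endpoint: "Relationship between ADA status and PK/PD, safety, and efficacy". No landmark, time-dependent status, common ascertainment window or rule that ADA must precede the outcome is given.

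Scheduled sampling is tied to dosing (Section 1.3, Table 2 and its footnote d). There is a pre-dose sample in each of Cycles 1 to 5. From then until 6 months, "PK and ADA samples will be taken on Day 1 of each cycle". After that, samples fall only at tumor-assessment cycles, with further samples at end of treatment and at the 90-day safety visit. Table 2 also triggers ADA samples at a Grade 2 or higher infusion reaction, a hypersensitivity event, a Grade 3 or higher event that causes a dose to be cut or interrupted, and a DLT. Section 8.6 likewise adds samples for Grade 2 or higher infusion reactions and "in participants with clinical signs of hypersensitivity reaction, in particular immune-complex reactions".

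On-treatment PFS runs from Cycle 1 Day 1 (Section 9.4.2).

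**The concern.** The PFS clock starts before ADA status is known, and status is settled by later samples whose number depends on how long the participant stays on treatment. A participant who progresses at the first scan has few chances to be found positive; one treated for a year has many. Time spent progression-free before the first positive sample is credited to the positive group, which is immortal-time bias. The end-of-treatment and 90-day samples can also turn someone positive after progression has been recorded.

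Section 8.6 anticipates that ADA may reduce efficacy. A bias in the opposite direction could offset a real loss and make ADA look harmless.

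Safety has a separate problem of ordering. A sample taken because an event occurred can make the participant positive, and that status can then be related to the same event.

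**Working it through.** The plan states no ADA rate, onset time or effect size for this comparison, so it has no figure to reproduce.

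**Step 1: samples by time on treatment.** Inputs are the Table 2 schedule, 21-day cycles, scans every 8 weeks in year 1 and every 12 weeks thereafter, and a 24-month cap. Scheduled post-baseline samples are the pre-dose samples after Cycle 1 up to the last dose, plus two (end of treatment and 90 days).

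- Cycle 1 dose only: 0 + 2 = 2
- last dose Cycle 3: 2 + 2 = 4
- dosing to about 6 months (Cycle 9): 8 + 2 = 10
- dosing to 24 months: 15 + 2 = 17

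**Step 2: chance of being ever positive.** With k samples and an assumed chance q of a positive per sample, independent of outcome, P = 1 − (1 − q)^k.

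| q (assumed) | k = 2 | k = 4 | k = 10 | k = 17 |
|---|---|---|---|---|
| 1% | 2.0% | 3.9% | 9.6% | 15.7% |
| 3% | 5.9% | 11.5% | 26.3% | 40.4% |
| 5% | 9.8% | 18.5% | 40.1% | 58.2% |

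The gradient comes from time on treatment alone.

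**Step 3: effect on PFS when ADA truly does nothing (HR = 1).** Simulation of 20,000 participants per scenario with the schedule above. Assumptions, none from the documents: 50% can develop ADA; ORR 15%; median time to progression 56 or 112 days in non-responders; median survival after progression 150 days; median ADA onset 3 to 32 weeks. Each cell gives the 56-day result, then the 112-day result.

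| Median onset | Ever-positive HR | Landmark C4D1 HR | Time-varying HR |
|---|---|---|---|
| 3 weeks | 0.91, 0.96 | 1.01, 1.01 | 1.00, 1.00 |
| 8 weeks | 0.78, 0.83 | 0.99, 1.01 | 0.99, 1.01 |
| 16 weeks | 0.67, 0.71 | 1.02, 1.01 | 0.96, 0.98 |
| 32 weeks | 0.63, 0.63 | 1.05, 1.01 | 1.00, 0.97 |

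Every scenario favours ADA-positives. ORR is 15.4% to 24.6% in positives and 11.9% to 14.8% in negatives. At 16-week onset with the 112-day setting, median PFS is 226 versus 157 days.

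A later-onset setting (15% to 50% positive by 6 months, median PFS 6 to 12 weeks) gives 0.53 to 0.73. Repeating both settings gave 0.51 to 0.71 for late onset and 0.66 to 0.97 for onset at 3 to 32 weeks, with the landmark at 0.92 to 1.04. The overall range is therefore about 0.5 to 0.97.

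**Step 4: triggered samples.** At q = 3%, one extra sample moves P(ever positive) from 5.9% to 8.7% after 2 scheduled samples (1 − 0.97^3), and from 26.3% to 28.5% after 10 (1 − 0.97^11).

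**Step 5: what a landmark leaves.** Parts A and B allow about 90 + 50 = 140 participants. Take 30% positive by 26 weeks with exponential onset, and half progressed by the week-8 scan. The share positive by week 9 is 1 − 0.70^(9/26) = 11.6%, so 140 × 0.5 × 0.116 is about 8 ADA-positives at the landmark.

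**The case against.** The strongest reply is that Section 9.4.5 does not commit to any comparison. The analysis is optional, its endpoint is exploratory, and Section 9.1 plans no formal model or test. Section 4.1 bases the MTD and RP2D on safety, tolerability and PK/PD. All of that stands and limits the severity. It does not remove the problem, because the only ADA status defined is the biased one.

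The size is also uncertain. If ADA appears at about 3 weeks, the distortion is 0.91 to 0.97 and hardly matters. The 15%-to-50%-by-6-months setting implies median onset of about 111 to 26 weeks, so it covers only late onset. A reader might take a hazard ratio near 0.6 as the expected error; the documents give no onset data to support that.

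A reader might also infer that longer survival drives the efficacy bias, or that event-triggered samples add to it. Neither is supported. Routine ADA sampling ends 90 days after the last dose, so time on treatment is the driver. Triggered samples bear on the safety comparison, where they make ADA-positives look worse. For infusion reactions in the first 6 months they add little, because a pre-dose sample is already due on the infusion day.

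Section 8.6 pairs a PK sample with every ADA sample, so loss of exposure can be examined without the PFS contrast. That is a useful complement, but it does not repair the contrast. Finally, neither remedy deals with confounding by dose level or by intra-patient dose increases (Section 4.1.2.2). That also stands.

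**Conclusion.** The point holds in a limited form. If the optional efficacy comparison uses the status defined in Section 9.4.5, it is biased in favour of ADA-positives. With no true effect, the false PFS hazard ratio is about 0.5 to 0.97: near 1 if onset is about 3 weeks, and about 0.5 to 0.7 if onset is late. The direction follows from the sampling schedule and the PFS time origin; the size rests on the assumptions listed. Masking of a real loss of efficacy is a possibility that follows from the direction. Only the no-effect case was simulated, so masking was not demonstrated.

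The safety issue is separate, small, and runs against ADA-positives. A reader might conclude that a primary result or the dose recommendation is compromised; the documents do not say that either depends on this analysis. Severity is minor to moderate.

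**What to change.** Amend Section 9.4.5 as follows.

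- **Incidence:** keep the ever-positive definition for this purpose only.
- **PFS and other time-to-event efficacy endpoints:** make ADA a time-varying covariate as the main method, switching to positive at the date of the first qualifying sample. Samples taken after progression then cannot affect PFS.
- **Sensitivity analysis:** use status from scheduled samples up to Cycle 4 Day 1, among participants still progression-free then.
- **Safety:** relate each event only to ADA status from samples taken before it, and list event-triggered samples separately so that they remain available for investigating hypersensitivity.
- **Population:** "The immunogenicity analyses will include all participants with at least one ADA assessment", which can be a baseline sample alone. State how participants with no post-baseline sample are handled, so that they are not counted as negative by default in these comparisons.

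The cost is SAP wording and programming on data already collected, with no new samples, visits or participants. The landmark drops early progressors and may leave only about 8 ADA-positives under the assumptions in Step 5, which is why it should not be the main method. Results should be described as exploratory and unadjusted for dose unless dose is included.
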